Study design		Using a traditional "3+3" dose-escalation design, subjects will be sequentially assigned to one of three dose groups (2.8×10^{10} units, 1.4×10^{11} units, and 7.0×10^{11} units per dose, once daily, with continuous intranasal instillation for 4 days). Each dose group will include 3 subjects, who will be enrolled one by one. The exploration of the next dose can only proceed if no dose-limiting toxicity (DLT) is observed in the 3 subjects. If 1 out of the 3 subjects experiences DLT, an additional 3 subjects will be enrolled in the same dose group; the exploration of the next dose can only move forward if no DLT is observed in these newly added 3 subjects. A minimum of 6 and a maximum of 18 subjects will be recruited during the dose exploration phase. Patients will receive other standard medical treatments in accordance with the recommendations in the 2022 Chinese Guidelines for Secondary Prevention of Ischemic Stroke and Transient Ischemic Attack , including antiplatelet drugs or anticoagulants, antihypertensive drugs, lipid-lowering drugs, and glucose-lowering drugs.
Outcome Measures	Primary Outcome Measure	Dose-Limiting Toxicity (DLT) Related to hUC-MSC-sEV-001 Includes: (1) Grade 3-4 severe adverse events occurring on day 14 (+-2), graded according to Common Terminology Criteria for Adverse Events (CTCAE) V5.0; (2) NIHSS score increase of ≥ 4 from baseline on day 14 (+-2); NIHSS score assessed by a professional rehabilitation physician;(3) Symptomatic intracranial hemorrhage occurring on day 14 (+-2); detected via CT scan and patient symptom presentation.
	Secondary Outcome Measures:	Serious adverse events related to the investigational drug within 90 (+-7) days. Distribution of Modified Rankin Scale (mRS) Scores within 90 (+-7) days. Barthel Index within 90 (± 7) days. Five-level, five-dimensional EuroQol (EQ-5D-5L) . Proportion of Modified Rankin Scale (mRS) Scores of 0-2 within 90 (+-7) days. All-cause mortality at 90 (+-7) days. Changes in infarct volume at 14 (+-2) days compared to baseline. Change from Baseline in National Institutes of Health Stroke Scale (NIHSS) Score.
Follow-up duration		Baseline (0~1 day), 7 (± 1) days, 14 (± 2) days, 90 (± 7) days
Sample size		6-18 subjects need to be included.

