- Their condition of a concurrent disease (excluding the index stroke) deteriorates, requiring alternative treatment that conflicts with the study protocol; if the subject's stroke condition deteriorates after receiving hUC-MSC-sEV-001 (e.g., progression of neurological deficit), they shall withdraw from the study and be classified as an invalid case (not a lost-to-follow-up case);
- They have poor compliance (e.g., missed ≥ 2 scheduled visits, refusal to undergo required assessments) or express unwillingness to continue the study;
- They are lost to contact for ≥ 2 weeks despite repeated attempts (e.g., telephone, text message, home visit).

For lost-to-follow-up subjects, the investigator shall make every effort to complete the final safety assessment (e.g., vital signs, adverse event recording) and document the reason for withdrawal in the CRF.

(5) Provisions for Excluded Cases

A case is excluded from the efficacy analysis set if:

- The subject is misdiagnosed (e.g., final diagnosis is transient ischemic attack rather than ischemic stroke);
- The subject meets the inclusion criteria but is not administered any dose of hUC-MSC-sEV-001, or fails to receive scheduled doses due to production failure of the study drug;
- The subject participates in another interventional clinical trial during the study period;
- The subject receives prohibited combined medications (e.g., antineoplastic drugs, neurotrophic factors) or non-protocol-specified treatments that affect efficacy assessment;
- The subject has no evaluable efficacy data (e.g., no post-baseline NIHSS or mRS assessment);
- The subject has severe protocol violations (e.g., administration of the wrong dose, missed ≥ 3 doses).

Excluded cases shall be documented in the "Protocol Deviation Log", and their CRFs shall be retained for audit. Subjects who receive at least one dose of the study drug and have safety data shall be included in the safety analysis set.

(6) Criteria for Terminating or Withdrawing from the Study

i. Study Termination

Study termination refers to the early cessation of the entire study before completion of the planned protocol. The decision to terminate the study shall be made by the sponsor, principal investigator, or Ethics Committee, and shall be documented in the "Study Termination Report". Reasons for termination include:

- Emergence of SAEs that suggest a causal relationship with the study drug and pose a serious risk to subjects;

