- Confirmation of the MTD or identification of an unsafe dose level;
- Major flaws in the study design that affect data validity;
- Regulatory requirements (e.g., request by the National Medical Products Administration [NMPA]).

. Subject Withdrawal

Subjects may withdraw from the study at any time for the following reasons:

(1) Investigator-determined withdrawal:

① The subject develops a medical condition that makes continued participation unsafe (e.g., severe allergic reaction, intracranial hemorrhage);② The subject uses medications that interact with the study drug (e.g., immunosuppressants) or affect efficacy assessment (e.g., edaravone);③ The subject experiences a SAE that requires termination of study participation;④ The subject has poor compliance that compromises the reliability of safety or efficacy data.

(2) Subject-initiated withdrawal:

① The subject voluntarily requests to withdraw (no reason required);② The subject is lost to follow-up (no contact for ≥ 2 weeks).

For withdrawn subjects, the investigator shall conduct a final safety assessment (if possible) and document the reason for withdrawal in the CRF. Subjects who withdraw due to AEs/SAEs shall receive appropriate medical treatment, and follow-up shall continue until the AE/SAE resolves or stabilizes.

(7) Criteria for Terminating the Study

The study will be terminated immediately if any of the following occurs:

≥ 2 subjects experience DLT at the same dose level (indicating that the dose exceeds the MTD);

- Production of hUC-MSC-sEV-001 fails to meet quality standards for 3 consecutive batches, resulting in inability to administer scheduled doses;

- The study drug is found to have no clinical benefit (e.g., no improvement in neurological function in all enrolled subjects) or is associated with unexpected severe toxicity;
- A major protocol deviation is identified (e.g., incorrect randomization, unapproved dose modification) that invalidates the study results;
- The sponsor terminates the study due to funding, strategic adjustments, or other reasons;
- The Ethics Committee or NMPA issues an order to terminate the study.

3. Intervention Measures

(1) Trial Drug

- **Generic Name:** Human Umbilical Cord Mesenchymal Stromal Cell-Derived Small Extracellular Vesicle (hUC-MSC-sEV-001) Nasal Drops
- **Source:** Isolated and purified from the supernatant of hUC-MSCs cultured under GMP conditions

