2. Efficacy Assessments:

- Neurological scales: NIHSS, mRS, MBI, EQ-5D-5L;
- Infarct volume measurement (DWI) and CTP parameter analysis.

3. Documentation: Record combined medications, rehabilitation therapy, and schedule the Day 90 visit.

Fourth Visit (Day 90 ± 7)

1. Safety Assessments:

- Vital signs measurement;
- Laboratory tests: CBC, clinical chemistry, coagulation function, serum electrolytes, infectious disease screening, tumor markers, urinalysis, pregnancy test (if applicable);
- Imaging examinations: Chest X-ray, 12-lead ECG, DWI, FLAIR, CTA/CTP;
- Final AE follow-up (until 30 days after the last dose).

2. Efficacy Assessments:

- Neurological scales: NIHSS, mRS, MBI, EQ-5D-5L;
- Final infarct volume measurement and CTP parameter analysis.

3. Study Completion: Confirm completion of all assessments, and document any protocol deviations.

Items/Visits	Baseline (Day 0)	Day 7 (±1)	Day 14 (±2)	Day 90 (±7)
Sign Informed Consent Form	●			
Review Inclusion/Exclusion Criteria	●			
Collect Demographic & Clinical Data	●	●	●	●
Vital Signs	●	●	●	●
Urine Pregnancy Test	●			●
Hematology (CBC) *	●	●	●	●
Clinical Chemistry (Liver/Kidney Function, Glucose, Lipids) *	●	●	●	●
Coagulation Function (PT, INR, APTT, FIB)	●		●	●
Serum Electrolytes	●		●	●
Infectious Disease Screening (8 Items)	●		●	●
Tumor Markers (AFP, CA199, CEA) *	●		●	●
Urinalysis *	●	●	●	●

Items/Visits	Baseline (Day 0)	Day 7 (±1)	Day 14 (±2)	Day 90 (±7)
Chest X-ray	•		•	
12-Lead ECG	•		•	•
Cerebral Imaging (CT/MRI/CTA/CTP)	•	•	•	•
Neurological Scales (NIHSS, mRS)	•	•	•	•
Modified Barthel Index (MBI)	•		•	•
EQ-5D-5L Score	•		•	•
Record Adverse Events	•	•	•	•
Record Concomitant Medications	•	•	•	•
Record Rehabilitation Therapy	•	•	•	•

7. Regulations for Packaging, Acceptance, Storage, Distribution, and Recovery of Study MSC-sEV Preparations

(1) Packaging of Study MSC-sEV Preparations

- **Primary Packaging:** Sterile glass vials (2.0 mL) with rubber stoppers and aluminum caps, labeled with the study drug name, batch number, dose level, expiration date, storage conditions, and "For Clinical Trial Use Only".
- **Secondary Packaging:** Individual cartons containing one vial of study drug and one vial of hyaluronidase, with a leaflet describing the administration method.
- **Tertiary Packaging:** Insulated containers with dry ice for transportation, labeled with "Biological

Product", "Keep Frozen (-80°C)", and the sponsor's contact information.

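### Sections 2(4) and 2(6) define loss to follow-up differently, and both can close out a subject well before Day 90 without asking for the Day 90 outcomes

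*Protocol*

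**What the plan says.** **Section 2(4)**, on subjects lost to follow-up, lists several grounds. Two matter here. The contact ground reads: "They are lost to contact for ≥ 2 weeks despite repeated attempts (e.g., telephone, text message, home visit". The compliance ground reads: "They have poor compliance (e.g., missed ≥ 2 scheduled visits, refusal to undergo required assessments) or express unwillingness to continue the study".

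**Section 2(6)**, on subject withdrawal, restates the contact ground under subject-initiated withdrawal: "The subject is lost to follow-up (no contact for ≥ 2 weeks". No attempts are mentioned.

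**The schedule** in the synopsis is: "Baseline (0~1 day), 7 (± 1) days, 14 (± 2) days, 90 (± 7) days". In section 6, the last instruction at the Day 14 visit is: "Record combined medications, rehabilitation therapy, and schedule the Day 90 visit". No visit or call is listed between the two.

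**After loss**, section 2(4) asks for this and for the reason for withdrawal: "For lost-to-follow-up subjects, the investigator shall make every effort to complete the final safety assessment". Section 2(6) asks for the same where possible, and continues follow-up only for subjects who withdrew because of an AE or SAE. Neither section mentions Day 90 mRS or vital status.

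**Section 11(1)** fills missing efficacy data in the FAS by last observation carried forward (LOCF).

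**The concern.** Two weeks without contact, or two missed early visits, does not stop anyone from learning a subject's mRS or vital status at Day 90. A rule that ends follow-up on those grounds creates missing data that could have been avoided.

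The outcomes at stake are those in sections 5(2) and 5(3) that need Day 90 information:

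- mRS 0-2 at Day 90, which section 11(3) calls the primary efficacy endpoint;
- Day 90 NIHSS, MBI and EQ-5D-5L;
- all-cause mortality within 90 days.

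LOCF would put a value from Day 14 or earlier in place of a Day 90 value, in a condition where function may change between the two. It covers efficacy data only, so it supplies no vital status.

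**Working it through.** The protocol states no gap length or loss rate, so there is no figure of its own to reproduce. The check is calendar arithmetic on its visit windows.

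**Inputs** (synopsis and section 6): Day 7 window, Days 6-8; Day 14 window, Days 12-16; Day 90 window, Days 83-97. There are three post-baseline visits. A dose group has 3 subjects, or 6 if expanded (section 1(2)).

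**1. Interval with no scheduled contact** (Day 90 visit minus Day 14 visit)
- Shortest: 83 − 16 = 67 days
- Nominal: 90 − 14 = 76 days
- Longest: 97 − 12 = 85 days

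All are far above the 14-day limit. Section 8(2) continues AE monitoring to 30 days after the last dose (Day 3 + 30 = Day 33), but attaches no visit or call to it.

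**2. Contact ground as worded in section 2(6)**
- Last contact at Day 12: met on Day 12 + 14 = 26, which is 83 − 26 = 57 days before the Day 90 window opens
- Last contact at Day 16: met on Day 16 + 14 = 30, which is 83 − 30 = 53 days before

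A subject who follows the schedule exactly meets this wording.

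**3. Contact ground as worded in section 2(4)**

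Failed attempts are required. If the site first tries on Day 83, two weeks of failure end on Day 83 + 14 = 97, the day the window closes. Under this wording a subject is lost early only if the site tries and fails for two weeks during the interval.

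**4. Missed-visit example in section 2(4)**
- Days 7 and 14 missed: complete by Day 16, which is 83 − 16 = 67 days before the Day 90 window opens
- Days 7 and 90, or Days 14 and 90, missed: complete only once Day 90 itself is missed, so nothing is closed early

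**5. What is left to analyse**
- Lost after Day 14: the Day 14 score is carried to Day 90.
- Missed Days 7 and 14, then closed: only baseline can be carried forward, and section 2(5) excludes from the efficacy set a subject with no post-baseline NIHSS or mRS.
- Weight of one subject: 1/3 = 33% of a dose group of three; 1/6 = 17% of a group of six.

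**The case against.** The strongest reply is that section 2(6) is shorthand for the term section 2(4) has just defined. A reading that withdraws every compliant subject defeats the protocol's own schedule, so nobody would apply it. That is plausible, and a reader should not infer that the unscheduled interval by itself closes subjects out. Under section 2(4) it does not, because repeated attempts must first have failed. The two sentences still differ, and the one listed as a ground for withdrawal lacks the condition.

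Four further limits stand:

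- **The missed-visit count is an example of poor compliance, not a fixed threshold.** Section 2(6) ties compliance withdrawal to the reliability of the data. It is nevertheless the only number the site is given, and it can be met before Day 90.
- **Nothing expressly forbids collecting Day 90 data after loss.** That such data go uncollected is an inference from loss being handled as withdrawal with only a safety assessment sought. Section 10(3) makes completion of the Day 90 visit by all subjects a condition of database lock. That points towards pursuing the visit, but it does not say how this applies to a subject already recorded as withdrawn.
- **The DLT endpoint is untouched by the Day 14-90 gap.** DLT is assessed within 14 days of the first dose. A subject who missed both Day 7 and Day 14 would raise a separate DLT problem, which this rule does not cause.
- **Late drug-related SAEs are a different matter.** A reader might blame this rule for missing them. The main limit there is that AE monitoring ends about Day 33, whatever the loss rule says.

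**Conclusion.** The point holds in this form: the two definitions conflict, the section 2(6) wording does not fit the schedule, the missed-visit example can end follow-up by Day 16, and after loss no one is told to obtain Day 90 mRS or vital status. It concerns the Day 90 efficacy outcomes and 90-day mortality.

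The size is conditional. Each subject closed out early costs 33% of a three-subject group's Day 90 data, or 17% of six. The protocol gives no loss rate, so how often this would happen cannot be estimated. The conclusion assumes that a site reads loss as withdrawal and does only what the text then asks. A site that pursued Day 90 on its own initiative would avoid the loss. The change is worth making because it is small and the groups are too small to absorb avoidable missing data.

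**What to change.** 1. Use one definition in sections 2(4) and 2(6): at least two weeks without contact despite documented failed attempts.
2. Before Day 90, record a missed contact or missed visit as such and keep the subject in follow-up. Remove the two-missed-visits example as a ground for loss.
3. Settle loss for Day 90 outcomes only after the window closes (90 + 7 = Day 97).
4. Unless consent is withdrawn, still seek Day 90 mRS and vital status by telephone, video, home visit or records, from the subject or legal representative.

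Section 2(4) already names telephone and home visits for contact attempts, and section 8(6) names telephone and video for AE follow-up. Using them for mRS is an added procedure, so the mode of assessment should be recorded.

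The cost is a wording change, a few extra contacts in at most 18 subjects, and some mRS scores obtained remotely rather than in person.

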Single-center, prospective, dose-escalation clinical trial.

(2) Trial Administration Strategy

A traditional "3+3" dose-escalation design will be adopted. Subjects will be sequentially assigned to one of three dose groups (2×10^{10} units, 1×10^{11} units, 5×10^{11} units per administration, once daily for 4 consecutive days via intranasal instillation). Each dose group initially enrolls 3 subjects, with sequential enrollment (i.e., the next subject is enrolled only after the previous subject completes the 14-day DLT observation period).

- If no DLT is observed in 3 subjects of a dose group, the study proceeds to the next higher dose level.

- If 1 out of 3 subjects experiences DLT, an additional 3 subjects are enrolled in the same dose group. If no DLT is observed in the additional 3 subjects, the study proceeds to the next higher dose level; if ≥ 1 additional subject experiences DLT, the current dose level is defined as the maximum tolerated dose (MTD), and dose escalation is terminated.
- A total of 6 to 18 subjects will be recruited during the dose-escalation phase.

(3) Study Suspension or Early Termination

The study will be suspended or terminated early if any of the following occurs:

- Violation of the *Good Clinical Practice (GCP)* or the *Administrative Measures for Stem Cell Clinical Research (Trial)*;
- Emergence of new safety or efficacy data on MSC-sEVs indicating that the trial poses a serious risk to patient safety or is clearly ineffective;
- Failure to enroll subjects as scheduled for 3 consecutive months;
- Major protocol deviations that affect the validity of study data;
- Request for termination by the sponsor or regulatory authorities.

2. Subject Selection Criteria

(1) Inclusion Criteria

- Confirmed diagnosis of acute ischemic stroke (in accordance with the *Chinese Guidelines for the Diagnosis and Treatment of Acute Ischemic Stroke (2023)*);
- Aged 18-70 years, regardless of gender;
- Anterior circulation occlusion (internal carotid artery, middle cerebral artery M1/M2 segment) confirmed by CTA or MRA;
- mRS score of 0-1 before the current stroke episode (indicating no or minimal disability prior to the index event);
- ASPECTS ≥ 6 on non-contrast computed tomography (NCCT) or diffusion-weighted imaging (DWI) after stroke onset (indicating a small to moderate infarct volume);
- NIHSS score ≥ 6 at screening (indicating moderate to severe neurological deficit);

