1. **Dose Adjustment:** No dose reduction is allowed during the study. If a subject experiences a Grade ≥ 3 AE, study drug administration is suspended until the AE resolves to Grade ≤ 1 ; if the AE is judged to be related to the study drug, the subject withdraws from the study.

2. **Prohibited and Restricted Medications:**

- Prohibited medications: Antineoplastic drugs, immunosuppressants (e.g., cyclosporine, tacrolimus), neurotrophic factors (e.g., nerve growth factor);
- Restricted medications: Antibiotics and antiviral drugs (used only for confirmed infections, with duration documented); non-steroidal anti-inflammatory drugs (NSAIDs) (avoided if possible to reduce bleeding risk).

3. **Concurrent Diseases Management:** If a subject develops a concurrent disease (e.g., pneumonia, myocardial ischemia) during the study, the treating physician provides standard treatment, and the details are documented in the "Concurrent Disease Record Form" in the CRF.
4. **Subject Education:** Subjects are instructed to report any new symptoms (e.g., headache, nasal congestion, rash) to the investigator immediately, and to avoid self-medication with prohibited drugs.

4. Observation Items

(1) Demographic and Clinical Data

1. **Demographic Characteristics:** Gender, age, date of birth, ethnicity, dominant hand, occupation, height, weight, body mass index (BMI);
2. **Clinical History:** Chief complaint, onset time of stroke, detailed history of present illness, primary diagnosis (including infarct location), secondary diagnoses, past medical history (hypertension, diabetes, hyperlipidemia, coronary heart disease), surgical history, allergy history, family history, smoking history (pack-years), drinking history (alcohol consumption per week);
3. **Medication History:** Current medications (including over-the-counter drugs, herbal supplements) at screening, with dosage, frequency, and duration documented.

All data are recorded in the "Baseline Demographic and Clinical Data Form" in the CRF.

(2) Safety Observation Indicators

1. **Vital Signs:** Measured before each dose administration and at each follow-up visit:
 - Pulse (beats per minute), blood pressure (mmHg, measured in the sitting position after 5 minutes of rest), respiratory rate (breaths per minute), body temperature (°C, axillary or oral);
 - Abnormal vital signs (e.g., hypertension: systolic blood pressure ≥ 160 mmHg) are documented and followed up.
2. **Laboratory Tests:**

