1. Neurological Function Scales:

- **NIHSS:** Assesses the severity of neurological deficits (range: 0-42; higher scores indicate more severe deficits). Administered at baseline, Day 7, Day 14, and Day 90.
- **mRS:** Assesses functional independence (range: 0-6; scores 0-2 indicate good functional outcome). Administered at baseline, Day 7, Day 14, and Day 90.
- **Modified Barthel Index (MBI):** Assesses activities of daily living (range: 0-100; higher scores indicate better independence). Administered at baseline, Day 14, and Day 90.
- **EQ-5D-5L:** Assesses health-related quality of life (including mobility, self-care, usual activities, pain/discomfort, anxiety/depression; scored as a utility value ranging from -0.291 to 1.0). Administered at baseline, Day 14, and Day 90.

2. Cerebral Perfusion Parameters (CTP):

- Measured at baseline, Day 14, and Day 90: cerebral blood volume (CBV), cerebral blood flow (CBF), mean transit time (MTT), time to peak (TTP) in the infarct core and penumbra.
- Changes in perfusion parameters from baseline are used to evaluate the improvement of cerebral blood flow.

3. Infarct Volume Measurement:

- Infarct volume is measured on DWI using the ABC/2 method (A: maximum length, B: maximum width perpendicular to A, C: number of slices × slice thickness).
- Changes in infarct volume from baseline to Day 14 are used to evaluate infarct progression or regression.

5. Outcome Evaluation Indicators

(1) Primary Safety Endpoints

- **Dose-Limiting Toxicity (DLT):** Assessed within 14 days of the first dose, defined as any of the following:
 1. Grade 3-4 AE related to the study drug (CTCAE V5.0), such as severe nasal bleeding, anaphylactic reaction, or hepatic injury;
 2. Increase in NIHSS score ≥ 4 points from baseline (indicating significant neurological deterioration);
 3. Symptomatic intracranial hemorrhage (confirmed by CT/MRI and associated with neurological deterioration).

(2) Secondary Safety Endpoints

1. **SAE Incidence:** Proportion of subjects with drug-related SAEs within 90 days of the first dose;
2. **All-Cause Mortality:** Proportion of subjects who die from any cause within 90 days of the first dose;
3. **Laboratory Abnormality Rate:** Proportion of subjects with Grade ≥ 3 laboratory abnormalities (e.g., thrombocytopenia, elevated liver enzymes) within 90 days.

(3) Efficacy Endpoints

1. **Functional Outcome:** Proportion of subjects with mRS score 0-2 at Day 90;

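### A dosed subject can be withdrawn from the whole study to protect efficacy data, which may cut short the 14-day DLT observation and the 90-day safety follow-up

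*Protocol*

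**What the plan says.** Section 2(6), Subject Withdrawal, opens with "Subjects may withdraw from the study at any time for the following reasons". Among the investigator-determined grounds, item ② reads "The subject uses medications that interact with the study drug (e.g., immunosuppressants) or affect efficacy assessment (e.g., edaravone"). The part at issue is "or affect efficacy assessment (e.g., edaravone"). The withdrawal is from the study, not only from study drug or from an analysis set.

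The closing paragraph of section 2(6) sets what follows: "For withdrawn subjects, the investigator shall conduct a final safety assessment (if possible) and document the reason for withdrawal in the CRF". It requires further follow-up only for subjects who leave because of an AE or SAE.

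Section 2(5) deals with the same kind of subject at the analysis level. Its grounds for exclusion from the efficacy set include prohibited medication "or non-protocol-specified treatments that affect efficacy assessment". The same section keeps dosed subjects with safety data in the safety set.

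Section 3(4) states "Prohibited medications: Antineoplastic drugs, immunosuppressants (e.g., cyclosporine, tacrolimus), neurotrophic factors (e.g., nerve growth factor"). Edaravone is not named there, among the restricted medications, or in the exclusion criteria.

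**The concern.** The trial exists to judge safety and find a dose. DLT is the primary endpoint, and the secondary safety endpoints run to Day 90. Item ② allows safety observation to stop so that efficacy data stay clean, which reverses those priorities. The item also covers drugs that interact with the study drug. That half may have a safety rationale and is not in question here.

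The situation can arise without any rule being broken. Edaravone is on no list, and the standard treatments in section 3(2) are given as an open list. A subject could be enrolled and dosed while receiving edaravone, or start it later, and then be withdrawn because of it.

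The consequence reaches dose escalation. Section 1(2) states that "the next subject is enrolled only after the previous subject completes the 14-day DLT observation period", and it escalates when no DLT is seen in 3 subjects. It does not say what happens when a subject's 14 days are cut short for a reason unrelated to safety.

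**Working it through.** The protocol gives no figure for this point, so there is none to reproduce. The check is a reading of the text, followed by arithmetic on what one withdrawal costs.

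**What is observed after such a withdrawal**

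| Outcome | Window in the protocol | What section 2(6) secures |
|---|---|---|
| DLT (section 5(1)) | 14 days from first dose; the synopsis places the NIHSS and haemorrhage components at Day 14 (±2) | One final assessment, where feasible, at the time of exit |
| Drug-related SAEs (section 5(2)) | 90 days from first dose | Nothing beyond that assessment, unless the exit was due to an AE or SAE |
| Death: "Proportion of subjects who die from any cause within 90 days of the first dose" | 90 days from first dose | As above |

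An exit contact before Day 14 cannot supply the Day 14 NIHSS score or the Day 14 imaging.

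**One incomplete DLT observation in an initial cohort of 3**

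With no DLT among n subjects, the exact one-sided 95% upper limit for the DLT rate is 1 − 0.05^(1/n).
- n = 3: 1 − 0.05^(1/3) = 0.632
- n = 2: 1 − 0.05^(1/2) = 0.776

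The step from 63% to 78% assumes that the withdrawn subject is not replaced.

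**Effect on escalation if the withdrawn subject is counted as having had no DLT**

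This way of counting is an assumption, because the protocol is silent. Let p be the true DLT rate (assumed) and m the number of the first three subjects with complete observation:

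P(escalate) = (1 − p)^m + m·p·(1 − p)^(m−1)·(1 − p)^3

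| p | m = 3 | m = 2 | Rise (points) |
|---|---|---|---|
| 0.10 | 0.906 | 0.941 | 3.5 |
| 0.20 | 0.709 | 0.804 | 9.5 |
| 1/3 | 0.428 | 0.576 | 14.8 |
| 0.50 | 0.172 | 0.313 | 14.1 |

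For p = 1/3 and m = 3: 0.2963 + 0.4444 × 0.2963 = 0.428. For m = 2: 0.4444 + 0.4444 × 0.2963 = 0.576.

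**One subject lost to Day 90**

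With 6 to 18 subjects, this is 1/18 = 6% to 1/6 = 17% of the trial.

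**How often a cohort would be affected**

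Let q be the chance that a subject is withdrawn on this ground before Day 14. The protocol gives no value, so a range is assumed. The chance of at least one such loss in 3 subjects is 1 − (1 − q)^3.
- q = 0.02: 6%
- q = 0.05: 14%
- q = 0.10: 27%

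**The case against.** - **The clause is permissive.** Nothing obliges the investigator to withdraw a subject who takes edaravone, and harm needs several steps in a row. This stands. It limits how serious the point is, but it does not justify the rule.
- **AE monitoring runs on dosing.** Sections 4(2) and 8(2) monitor AEs until 30 days after the last dose. The last dose is on Day 3, so this reaches about Day 33, past the DLT window, with no exception for withdrawn subjects. AE-based DLTs might therefore still be captured. But the protocol does not say that monitoring continues after withdrawal, and such monitoring would supply neither the Day 14 NIHSS and imaging nor the outcomes to Day 90.
- **The figures rest on assumptions.** Section 1(2) can be read to mean that two complete observations do not satisfy the rule for three, in which case the site would enrol another subject. That reading is reasonable, but it is not written down. The figures show what is at stake under stated conditions; they do not predict an escalation error.
- **The wider gap is elsewhere.** Voluntary withdrawal, poor compliance and loss of contact also end observation, and the protocol has no general rule on DLT evaluability or replacement. This is true, and removing the clause will not close those routes. But several of them are beyond the investigator's control, whereas this one is created by the protocol.

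**Conclusion.** The concern holds. Section 2(6) item ② permits withdrawal from the study for a reason that concerns efficacy only, while section 2(5) already gives efficacy the protection it needs. The clause puts 14-day DLT observation and 90-day SAE and mortality outcomes at risk with no safety or analytic gain.

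Per event, the cost is one of three DLT observations in an initial cohort, or 6% to 17% of the trial's Day 90 safety follow-up. The effect on the upper limit assumes no replacement and no observed DLT. The effect on escalation assumes that the subject is counted as free of DLT. The frequency is unknown. Because withdrawal is discretionary, this is a change that should be made rather than a fatal defect.

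**What to change.** In section 2(6), item ②, delete the clause on drugs that affect efficacy assessment, together with its edaravone example. Keep the clause on drugs that interact with the study drug. Add wording such as:

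> Use of a medication that may confound efficacy, for example edaravone, is recorded in the CRF and handled in the efficacy analysis under section 2(5). It is not a reason to leave the study. The subject completes the Day 14 DLT assessment and safety follow-up to Day 90.

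If the sponsor regards edaravone as a confounder, name it in the prohibited list in section 3(4). A sentence in section 1(2) on who is evaluable for DLT, and when a subject is replaced, would also cover the other withdrawal routes.

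The cost is a change of wording. Day 14 and Day 90 are already scheduled, so no visits are added. The downside is that some subjects followed to the end will have efficacy data flagged as confounded, which section 2(5) already provides for.
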